
AE	Adverse Event
AR	Adverse Reaction
CF	Consent Form
CI	Chief Investigator
CRF	Case Report Form
CTR	Centre for Trials Research
cv	Curriculum Vitae
DREFAQ	Dresden Falls Questionnaire
FoG	Freezing of Gait
GCP	Good Clinical Practice
ISF	Investigator Site File
ISRCTN	International Standard Randomised Controlled Trial Number
MoCA	Montreal Cognitive Assessment
NHS	National Health Service
OxPAQ	Oxford Participation and Activities Questionnaire
PD	Parkinson's disease
PDQ-8	Parkinson's Disease Questionnaire 8
PI	Principal Investigator
PIC	Participant Identification Centre
PIS	Participant Information Sheet
PROMS	Patient Reported Outcome Measures
QA	Quality Assurance
QC	Quality control
QoL	Quality of Life
RCT	Randomised Controlled Trial
REC	Research Ethics Committee
SAE	Serious Adverse Event
SOP	Standard Operating Procedure
TIDieR	Template for Intervention Description and Replication
тм	Trial Manager
TMF	Trial Master File

TMG	Trial Management Group	
TSC	Trial Steering Committee	
TUG	Timed Up and Go	
UPDRS	Unified PD Rating Scale	

1 Amendment History

The following amendments and/or administrative changes have been made to this protocol since the implementation of the first approved version.

Amendment No.	Protocol version no.	Date issued	Summary of changes made since previous version

2 Synopsis

Short title	Evaluating the feasibility of a samba percussion intervention for people with			
	Parkinson's disease (PD)			
Acronym	SParky Samba			
Funder and ref.	Jacques and Gloria Gossweiler Foundation			
Trial design	Feasibility Randomised Controlled Trial (RCT)			
Trial participants	Patients with Parkinson's disease (PD)			
Planned sample size	Feasibility RCT, n = 60 (30 in intervention group, 30 in activity as usual)			
Planned number of sites	4			
Inclusion criteria	People diagnosed with PD			
	Age 18 or older			
	Able to provide consent to take part			
Exclusion criteria	Has already taken part in a SParky Samba group			
Intervention duration	12 weeks			
Planned trial period	Planned recruitment time from April 2025 – February 2026			
Primary objectives	Determine feasibility of testing the SParky Samba intervention in a feasibility RCT.			
Secondary objectives	Explore the effect of the SParky Samba intervention as compared to activities as usual across function and wellbeing of people with PD.			
Primary outcomes	 Feasibility of participant recruitment and retention and intervention adherence according to pre-specified criteria. 			
Secondary outcomes	 Unified PD Rating Scale (UPDRS) Freezing of Gait Questionnaire (FoG) Dresden Falls Questionnaire (DREFAQ) MiniBEST Test Montreal Cognitive Assessment (MoCA) 			

	PD Questionnaire 8 (PDQ-8)	
	 Oxford Participation and Activities Questionnaire (OxPAQ). 	
	Lorig Self Efficacy Scale	
	Physical Activity Scale for the Elderly (PASE)	
Intervention	SParky Samba group activity; weekly sessions lasting between 1 hour for 12 weeks.	

[figure not shown]

[figure not shown]
3 Trial Summary & Schema

3.1 Sparky Samba Study Overview

Phase 1 was conducted separately. This protocol is for Phase 2 of the study

3.2 Participant Flow Diagram

3.3 Trial Lay Summary

Parkinson's disease (PD) affects areas of the brain that are important for regulating many vital functions including movement, thinking, mood, sleep and pain. Symptoms progress over time, reducing independence, wellbeing and quality of life (QoL). Treatments are available that reduce some symptoms, but no proven treatment can slow or stop the decline. Treatments include medication and surgery, or lifestyle changes, commonly known as non-drug interventions. People with PD have highlighted the need for more interventions to help combat the movement problems and other symptoms they experience.

Interventions that include physical activity (exercise, physiotherapy, dancing) or repetitive beats to music, known as rhythmic auditory stimulation, have been shown to help with PD symptoms. Largely these have been delivered and tested in clinical settings. We know that community-based interventions can have positive health benefits. It has been suggested that providing interventions in the community, rather than in clinical settings, will help people with PD stay engaged with the intervention to achieve maximum and sustainable potential health benefit.

SParky Samba Trial

Our research team has been working with a group that has developed a new community-based samba percussion activity (SParky Samba). This has been designed for people with PD by people with PD, with the support of a samba band leader. An initial qualitative evaluation has shown that the people with PD attending SParky Samba experience several benefits in their movement, health and wellbeing from participating in the group. We want to perform an evaluation of SParky Samba to see if it has potential to help improve health outcomes and wellbeing in people with PD.

Firstly, to understand what the key parts of SParky Samba are, we have undertaken a series of observations of the SParky Samba group and interviews with group members. We have used this information to define SParky Samba as an intervention so that it can be delivered to new groups of people with PD.

Now we want to undertake a feasibility trial of the SParky Samba intervention in people with PD at different community SParky Samba groups in Wales. We will recruit 60 participants to take part in the trial. A computer programme will randomly determine whether they should either attend a SParky Samba group or a be part of an activity as usual (control) group for 12 weeks. We will measure movement, thinking and wellbeing at the beginning and end of the 12 weeks. We will also record how many people are willing to join and then stay in the trial. This will provide important information that

will help us design a bigger clinical trial to see if the SParky Samba intervention definitely affects the health and wellbeing of people with PD.

4 Background

Parkinson's disease (PD) is the second most common neurodegenerative disorder after Alzheimer's disease, that causes cell loss in the brain largely due to the abnormal aggregation of the alphasynuclein protein. In PD, atrophy of dopaminergic cells in the substantia nigra leads to progressive decline of motor function alongside changes in cognition, sleep, mood and other non-motor symptoms. There are no disease modifying therapies, with treatment options primarily supporting motor-symptom management, and often with significant side effects that worsen other PD symptoms. Stakeholder research prioritisation exercises demonstrate the need for developing non-pharmacological interventions that may aid both motor and cognitive functions (1,2) and allow tailoring for disease stage (3).

Common non-pharmacological interventions shown to have both motor and non-motor benefits for people with PD include physical activity in the form of targeted exercise (4,5) or other forms of movement such as dancing (6) or music-based movement therapy(7) as well as neurological music therapy in the form of rhythmic auditory stimulation (RAS) (8). RAS can be achieved through activities such as walking to a rhythmic beat or drumming and similar forms of music-based therapy, which have shown promising effects on gait and mobility in people with PD (9–11). The majority of these interventions have been trialled in clinical settings, but it is recognised that community-based activities promoting healthy behaviours in people with PD are likely to have greater long-term impacts (12–14) due to their enhanced accessibility and effects of social cohesion.

SParky Samba Initiative

A recently established PD specific samba percussion group 'SParky Samba' is a patient initiative led; designed by people with PD for people with PD and supported by a samba percussion tutor. This group activity combines RAS activities with social stimulation. Awareness of SParky Samba has gained momentum amongst people with PD who have indicated a need for more similar groups in other local communities. An initial qualitative evaluation of SParky Samba, conducted by our group (unpublished data) has highlighted its potential utility as a community-based activity for people with PD to improve social connectedness, wellbeing, physical activity participation and cognition. As indicated by our trial research partner, people with PD like therapeutic activities and lifestyle interventions that they

themselves, can control. Patient-led research is essential to develop interventions that have a better chance of successfully translating into practice because they are inherently acceptable, meaningful and relevant to those they have been developed for (15–17).

We have conducted an ethnographic study of the existing SParky Samba group in Cardiff, with follow-up stakeholder workshops in order to: 1) identify core intervention components (duration, exercises, movements) in preparation for intervention delivery; 2) refine intervention components, and determine intervention flexibility and how this may be adapted for individuals; 3) describe and specify the resulting intervention in detail according to the TIDieR framework (18); 4) create a logic model and identify a 'theory of change' regarding intervention mechanisms (how it may work), including the core elements of the music-based rhythms and pieces in terms of tempo, complexity, syncopation, use of beaters as metronomes which may affect mechanisms of change. This could be facilitating movement and impacting mood and reward, summarising inputs and resources, implementation strategies, outcomes, impact and context.

4.1 Rationale for Current Trial/Justification of Treatment Options

SParky Samba has achieved support from the PD community (individuals, the UK's leading PD charity PDUK) and arts-based funders, but it warrants further investigation for its potential health benefits. The SParky Samba intervention will be compared to an activities as usual control group. This will help to differentiate between the community and social potential benefits of standard social activities versus the specifics of the SParky Samba intervention and potential benefits of RAS.

Research Aim: Evaluation the feasibility of SParky Samba in a small-scale randomised controlled trial (RCT) as the next step towards a full effectiveness evaluation of SParky Samba.

5 Trial Objectives/Endpoints & Outcome Measures

5.1 Primary Objectives

Determine feasibility of testing the SParky Samba intervention in a feasibility RCT.

5.2 Secondary Objectives

 Explore the effect of the SParky Samba intervention as compared to an active social control across function and wellbeing of people with PD.

5.3 Primary Outcome Measure

Feasibility of participant recruitment and retention and intervention adherence according to prespecified criteria

	Progression Criteria				
		Red	Amber	Green	
Recruitment	No. approached willing to participate				
	(number consented/ number				
	approached)	<5%	5-19%	≥20%	
		< 24 in			
	No. recruited	total	25-44	45-60	
Retention	No of participants completing primary				
	end point	<50%	51-89%	≥90%	
	% Participants adherent to the				
Adherence	intervention (as defined in section 11.1)	<50%	51-79%	≥80%	
	% Participants completing at least 90%				
	of available baseline measures	<70%	71-94%	≥95%	
Data	% Participants completing at least 90%				
Completeness	of follow up measures	<50%	51-74%	≥75%	

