15.1 Main Analysis

Key demographic data will be summarised using descriptive statistics. For feasibility outcomes, recruitment will be assessed as the percentage of eligible people who provide consent to participate in the trial; retention as the percentage of participants recruited who complete the 12-week follow-up assessment; adherence as the percentage of recommended intervention or social control sessions completed. Feasibility criteria will be assessed according to a traffic light system with green (proceed to full effectiveness RCT) if all criteria listed in section 5.3 are in the green zone; amber (requiring adjustment before proceeding to full RCT) if all criteria are either in the amber or green zone; and red (do not progress to full RCT unless major changes are implemented) if at least one criterion is in the red zone. For secondary outcome measures we will calculate descriptive summaries such as mean and standard deviation, and 95% confidence intervals of participants' percentage changes from baseline to 12-week follow-up. This will provide estimates of effect size and variability of drumming-induced changes for use in power calculations for a future RCT.

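### The progression bands in section 5.3 are not contiguous: 24 recruited, 50% and 70% have no colour, so the section 15.1 rule can fail to give a verdict

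*Protocol*

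**What the plan says.** The primary outcome is feasibility judged against pre-specified criteria, and the table in Protocol section 5.3 holds those criteria. Its six rows (red, amber, green) read:

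- consented out of approached: "approached) <5% 5-19% ≥20" per cent;
- number recruited: red below 24, then "total 25-44 45-60" for amber and green;
- retention: "end point <50% 51-89% ≥90" per cent;
- adherence: "intervention (as defined in section 11.1) <50% 51-79% ≥80" per cent;
- baseline completeness: "of available baseline measures <70% 71-94% ≥95" per cent;
- follow-up completeness: "of follow up measures <50% 51-74% ≥75" per cent.

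Section 15.1 gives the overall verdict. It is green if every criterion is green, "amber (requiring adjustment before proceeding to full RCT) if all criteria are either in the amber or green zone", and red if at least one criterion is red. Red means no full trial unless major changes are made. The protocol has no rounding rule for these percentages and no default for a result outside the printed bands. The planned size in the Synopsis is "Feasibility RCT, n = 60 (30 in intervention group, 30 in activity as usual").

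**The concern.** A traffic-light rule works only if every possible result has exactly one colour. Only two of the twelve joins in this table are closed: 5% for the consent rate and 44/45 for the number recruited. At each of the other ten, a value or interval lies in no band.

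These bands are the primary outcome and the only progression rule in the protocol. A result in a gap would have to be coloured by judgement once it is known, which is the discretion that pre-specified thresholds are meant to remove. At the lower joins the open choice is between amber and red. At the upper joins it is between green and amber.

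**Working it through.** **Inputs.** The bands are those printed in section 5.3. The denominators come from the Synopsis: 60 for retention and completeness, 30 for adherence. Two assumptions: adherence is taken as the share of intervention-arm participants who meet the section 11.1 definition, and the consent rate as consented out of approached, both as in section 5.3.

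**Step 1: lower joins at the planned sizes.** Each count x out of n is converted to 100·x/n and compared with the bands.

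| Criterion | Last red | No colour | First amber |
|---|---|---|---|
| Number recruited | 23 | 24 | 25 |
| Retention, n = 60 | 29/60 = 48.3% | 30/60 = 50% | 31/60 = 51.7% |
| Adherence, n = 30 | 14/30 = 46.7% | 15/30 = 50% | 16/30 = 53.3% |
| Baseline completeness, n = 60 | 41/60 = 68.3% | 42/60 = 70% | 43/60 = 71.7% |
| Follow-up completeness, n = 60 | 29/60 = 48.3% | 30/60 = 50% | 31/60 = 51.7% |

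At other sizes the gap also catches values between the whole numbers, for example retention 30/59 = 50.85% and baseline completeness 41/58 = 70.69%.

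**Step 2: does whole-percent rounding help?** Not for the five results in step 1: 24 is a count, and 50% and 70% are already whole numbers. Rounding can even move a red result into a gap: baseline completeness of 32/46 = 69.57% is red unrounded but rounds to 70%, which has no colour.

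**Step 3: upper joins at the planned sizes.** No count falls in a gap:

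- retention: 53/60 = 88.3%, then 54/60 = 90%;
- adherence: 23/30 = 76.7%, then 24/30 = 80%;
- baseline completeness: 56/60 = 93.3%, then 57/60 = 95%;
- follow-up completeness: 44/60 = 73.3%, then 45/60 = 75%.

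**Step 4: upper joins at other sizes, unrounded.** Gaps are reached at retention 52/58 = 89.7%, adherence 23/29 = 79.3%, baseline completeness 55/58 = 94.8% and follow-up completeness 43/58 = 74.1%. The consent rate is the exception, because its denominator is the number approached. With 60 consented, 19% < 100·60/m < 20% requires 300 < m < 315.8, so m = 301 to 315 (19.93% down to 19.05%). Whole-percent rounding closes all of these upper gaps.

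**Step 5: how likely is a direct hit?** This is an illustration: the true rates are assumptions, since the protocol gives none. The binomial probability is P(X = x) = C(n, x)·p^x·(1 − p)^(n − x).

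| Uncoloured result | p at the cut | Further away | Further still |
|---|---|---|---|
| 30/60 | p = 0.5: 10.3% | p = 0.6: 3.0% | p = 0.7: 0.05% |
| 15/30 | p = 0.5: 14.4% | p = 0.6: 7.8% | p = 0.7: 1.1% |
| 42/60 | p = 0.7: 11.2% | p = 0.8: 2.1% | p = 0.9: 0.001% |

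**Step 6: pass an uncoloured criterion through section 15.1.** If another criterion is red, the verdict is red and the gap does no harm. If all the others are amber or green, the result is not all green, not all amber or green, and has no red. None of the three definitions applies.

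**The case against.** The strongest reply is that the bands are printed in whole per cents, so the authors probably meant whole-percent reporting. Rounding conventions usually belong in the SAP, which is not shown. On that reading the upper joins are a matter of notation. Even unrounded, 89.7% fails the printed green bound and is clearly not red, so amber is the natural reading. This largely stands, and the upper gaps are the lesser part of the point. It does not help at 24, 50% and 70%, where rounding changes nothing and the printed table does not show which side was meant.

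A second reply is that a direct hit is unlikely unless true performance is near a red boundary. Step 5 bears this out. It limits how often the defect would matter, but those borderline cases are the ones the bands exist to settle.

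A reader might also infer three stronger things that the document does not support:

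- That any result in a gap leaves the trial without a verdict. If another criterion is red, section 15.1 still returns red.
- That the lower gaps decide between going ahead and abandoning a full trial. Red allows a full trial after major changes, and amber allows one after adjustment, so the difference is one of degree.
- That 24 belongs in red while 50% and 70% belong in amber. The protocol does not assign them, and nothing in it justifies treating the count differently from the percentages.

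**Conclusion.** The table is wrong as written. Five results at the planned sizes have no colour under either exact or whole-percent reading: 24 recruited, 30/60 for retention, 15/30 for adherence, 42/60 for baseline completeness and 30/60 for follow-up completeness. If percentages are not rounded, five amber/green joins (19–20%, 89–90%, 79–80%, 94–95%, 74–75%) have gaps as well. Apart from the consent rate, those are reached only at denominators other than 60 or 30.

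When a criterion falls in a gap and none of the others is red, the progression rule is undefined. With a true rate exactly at a red boundary, the chance of landing on the uncoloured count is about 10% to 14% per criterion, and it falls quickly away from the boundary. The adherence and consent-rate figures rest on the section 5.3 definitions. An SAP rounding rule alone would not cure the defect, because the cut points themselves are fixed in the protocol.

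**What to change.** Make each row of the section 5.3 table contiguous, with amber starting where red ends and running to just below the green bound. For retention this is <50% / ≥50% to <90% / ≥90%, and likewise for the other percentage rows.

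The trial team should place 24, 50% and 70% by one consistent rule. For example, keep the printed red bounds, so that red is <24, <50% and <70% and amber starts at 24, 50% and 70%. Add one sentence saying that banding uses unrounded percentages.

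Do this before any feasibility data are reviewed; waiting for data lock would be too late. The study is unblinded (section 14.2), screening logs reach the trial team monthly (section 9.2), and the steering committee receives a full report midway through recruitment (section 21.2). The cost is one reworded table and one sentence in a protocol amendment. Sample size, procedures and participant burden do not change.

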5.4 Secondary Outcomes Measures

- Unified PD Rating Scale (UPDRS) (19),
- Freezing of Gait (FOG) Questionnaire (20)
- Dresden Fall Questionnaire (DREFAQ) (21)
- MiniBEST Test (22)
- Montreal Cognitive Assessment (MoCA) short from [Espresso] (23)
- PD Questionnaire 8 (PDQ-8) (24)
- Oxford Participation and Activities Questionnaire (OxPAQ) (25,26)

- Lorig Self Efficacy Scale (26,27)
- Physical Activity Scale for the Elderly (PASE)(28)

6 Trial Design & Setting

This will be a parallel group feasibility RCT of the SParky Samba intervention compared to an activity as usual control group. A recruitment target of 60 people with PD will be randomised 1:1 to intervention or activity as usual. Participants will be recruited from a combination of specialist movement disorder clinics, via the PD specialist nurse network, social media advertising and advertising through local PD focused organisations such as Parkinson's UK Cymru. The SParky Samba intervention will be delivered across three principal community sites in Wales (Cardiff, Llandudno and Fishguard) with possible additional sites in Carmarthen and Chepstow, dependent on external funding. Outcomes will be assessed at baseline (prior to randomisation) and at the end of the 12 week intervention delivery period. Those randomised to the activity as usual group will be able to access SParky Samba after the completion of the 12 week follow-up assessments.

6.1 Risk Assessment

A Trial Risk Assessment has been completed to identify the potential hazards associated with the trial and to assess the likelihood of those hazards occurring and resulting in harm. This risk assessment includes:

- The known and potential risks and benefits to human subjects
- How high the risk is compared to standard practice
- How the risk will be minimised/managed

This trial has been categorised as low risk, where the level of risk is comparable to the risk of standard medical care. A copy of the trial risk assessment may be requested from the Trial Manager. The trial risk assessment is used to determine the intensity and focus of monitoring activity (see section 22.1).

7 Site & Investigator Selection

This trial will be carried out at participating sites within Wales local to existing SParky Samba groups.

Before any site can begin recruitment a Principal Investigator (PI) at each site must be identified. The following documents must be in place and copies sent to the SParky Samba Trial email account (see contact details on page 4):

- The confirmation of Capability &Capacity from the site's R&D Department following sharing of local information pack
- > Favourable opinion of host care organisation/PI from Main Ethics committee
- > A signed Trial Agreement
- Current Curriculum Vitae (CV) and GCP training certificate of the PI
- Completed Site Delegation Log
- Full contact details for all host care organisation personnel involved, indicating preferred contact
- ➤ A copy of the most recent approved version of the Participant Information Sheet(s) and Consent Form(s) on host care organisation headed paper
- A copy of the most recent Consent Form(s) on host care organisation headed paper
- Returned copy of the Self-Evident Correction Log signed by the PI.

Upon receipt of all the above documents, the Trial Manager (TM) will send written confirmation to the PI/lead Research Nurse detailing that the centre is now ready to recruit participants into the trial. This letter/email must be filed in each site's Site File. Along with the written confirmation, the site should receive anything relating to trial intervention and a trial pack holding all the documents required to recruit into the Trial.

Occasionally during the trial, amendments may be made to the trial documentation listed above. The CTR will issue the site with the latest version of the documents as soon as they become available. It is the responsibility of the CTR to ensure that they obtain local R&D approval for the new documents. Site initiation will be by attendance at a teleconference meeting online.

8 Participant Selection

Participants are eligible for the trial if they meet all of the following inclusion criteria and none of the exclusion criteria. All queries about participant eligibility should be directed to the TM before randomisation/registration.

